Phone Visit and Performance Check (2 weeks after baseline)

1. Study staff will contact the subject and parent/guardian to see how well the subject is adapting to the GSM brace and remind the subject/parent to remove the temperature monitor from the brace and send by courier overnight to the study site.
2. Safety Check: Query for adverse events and other issues
3. Performance Check – to ensure adherence to prescribed number of hours per day in the GSM brace:
 1. If any problems are noted during the phone contact the PI will determine whether adjustments to the brace could alleviate the issues and, if so, ask the subject return to clinic
 2. If the temperature monitor data indicate the subject is wearing the GSM brace an average of 2 or more hours less per day than prescribed
 - a. The PI will determine whether adjustments to the brace could alleviate the issues and have the subject return to clinic; if not, the subject will exit the study and return to their current TLSO
 - b. If after adjustments to the brace, the subject feels that the brace is still incompatible with the prescribed wear time, the subject will exit the study and return to their current TLSO

Phone Visits (Weeks 4, 6, 8, and 10 after baseline)

1. Study staff will contact the subject and parent/guardian to see how well the subject is adapting to the GSM brace and remind the subject/parent to continue completion and return of the diaries to the study site in the prepaid envelopes.
2. Safety Check: Query for adverse events and other issues

Visit 3 (3-4 months after baseline, approximately 1 hour)

1. Standing coronal full-spine radiographs out of the brace and measurement of the Cobb angle
2. Download of temperature monitor data from GSM brace
3. Collection of GSM Brace Diary
4. Completion of the Brace Questionnaire and the Italian Spine Youth Quality of Life (ISYQOL) questionnaire
5. Completion of GSM App Feedback Questionnaire (optional)
6. Safety Check: Query for adverse events and other issues
7. Performance Check:
 - a. If the Cobb angle measures no more than 10 degrees greater than that obtained from the subject's most recent out of brace radiograph (prior to enrollment), we will conclude the curve is stable or has progressed within the expected limit. If not, the subject will resume use of the TLSO.
 - b. If curve stabilization is seen, subjects may opt to continue the GSM brace or resume use of their TLSO based on subject and parent preferences.

Ongoing Evaluations after Visit 3 (following the standard-of-care until GSM brace is discontinued)

For subjects continuing to use the GSM brace after Visit 3: Subject clinical care and evaluations (x-rays, clinical exams) after Visit 3 will be limited to that typically performed as the standard of care (SOC). The exception to the SOC will be the administration of the BrQ and ISYQOL at the end of treatment, ongoing monitoring and recording of AE's discovered during routine clinic visits or other communications, and temperature monitoring (at sites where this is not typically SOC). Clinical and radiographic data from these visits will be collected for study purposes (height, weight, onset of menses, Cobb angle(s), kyphosis, lordosis, coronal and sagittal balance, apical vertebral rotation, in-brace Cobb angle(s), and skeletal maturity indicators) as available.

GSM brace treatment will be discontinued using individualized SOC parameters such as Cobb angle and skeletal maturity indicators, at which time the subject will exit the study.

Exit From Study

Subjects will exit the study upon occurrence of the following events

1. Visit 2. GSM in-brace Cobb is $>10^\circ$ more than the TSO in-brace Cobb
2. Subject not wearing or tolerating GSM brace (per temperature monitor reading 2 weeks after baseline, or at any time during study period)
3. Visit 3. GSM out-of-brace Cobb indicates curve progression
4. GSM brace is discontinued using standard of care criteria

Additional Information on Assessments

Radiographs and Assessments: When available, radiographs will be obtained using the EOS® Imaging system Micro Dose protocol. The EOS® system provides low dose, full body, stereoradiographic images of patients in a functional position. It is a bi-planar device using two perpendicular fan beams of X-rays and proprietary detectors that travel vertically while scanning the patient. In a few seconds, the EOS® exam produces two simultaneous frontal and lateral, low dose images of the whole body or an anatomical segment. The Micro Dose option for pediatric follow up exams further reduces the radiation exposure. <http://www.eos-imaging.com/us/professionals/eos/eos>.

Participating sites who do not have access to the EOS® Imaging system Micro Dose protocol are allowed to use their existing equipment. However, they are responsible for calculating the amount of research-related radiation and the potential risks, to include this information in IRB/human subjects research application materials, and to relate this information to the subject via the informed consent document as required by the IRB or equivalent review board.

In addition to the Cobb angle, other components of the deformity will be measured, including kyphosis, lordosis, apical vertebral rotation, and coronal and sagittal balance.

Spiropet

Vital capacity will be estimated using the Spiropet portable spirometer. Subjects will be instructed to inhale as deeply as possible and to then exhale completely over 5 to 6 seconds through the spirometer. This will be repeated 2 times, with a minimum of 30 seconds in between trials. Disposable mouthpieces are used to prevent contamination across subjects.

<https://www.fitnessmart.com/products/spiro-pet-small-dry-spirometer-model-64450?variant=29708592263>

Temperature Monitors to Estimate Brace Adherence

Participating sites are encouraged to use their standard-of-care brace temperature monitors/loggers. If the site has not been using a monitor to estimate brace wear, the sponsor will provide iButtons and the required hardware/software.

The iButton™ is a commercially available electronic device which records and stores time, date and temperature readings. The logger will be set to record date, time and temperature every 15 minutes. The temperature range at which the brace is assumed to be on will be set at 82.4°F and 110°F. Validation of the accelerometer data as an estimate of the number of hours per day that the subjects are wearing the brace will be done via comparison with data from a temperature logger. The reliability and validity of iButton™ data for estimating wear time has been demonstrated in several published reports.²⁷⁻²⁹ (iButton™ DS1922L”

https://www.thermochron.com/product/ds1921g-thermochron/?gclid=EA1aIQobChMI5t-G1K6G3QIVRMDICh1A2gDSEAAyASAAEgL1YvD_BwE (Maxim Integrated Products, Inc.; [name]).

Questionnaires

The Brace Questionnaire (BrQ, 34 items³⁰) and the Italian Spine Youth Quality of Life Questionnaire (ISYQOL, 20 items³¹) are validated measures of health-related quality of life in patients being treated for spinal deformities. An item directly asking the subject how much they like their brace was added for this study. The GSM Brace Diary was created specifically for this study based on the Scoliosis Compliance Questionnaire.¹⁷ The diary lists several daily activities (e.g. time at home, time at school, sports, being with friends, walking, bending, taking brace on and off) and asks the subject to rate how challenging they were that day on a 5-point Smiley Face scale from laughing to crying. The diary also includes questions about pain and discomfort in the brace, and a free text area for the subject to record any other comments they have related to brace wear.

GSM Brace Mobile App (optional)

Subjects will be able to opt in or out of use of the app. The app was developed by GSM specifically for this pilot and is available free-of-charge to interested subjects. The app is available for IOS and Android via the App Store and Play Store. Security functions have been built into the app to maintain confidentiality, integrity and availability as referenced by the NIST cybersecurity framework, HIPAA and the FDA. Updates are validated through Apple and Google stores. The app is not intended for use in the diagnosis of disease or other conditions, or in the cure, mitigation or treatment or prevention of disease and is therefore not considered a medical device and is outside of FDA purview. According to FDA guidance, the app poses minimal risk to the user as it is solely intended to help users self-manage their disease (track brace wear time) and does not provide any specific treatment suggestions.

The mobile app connects to the sensor in the brace and downloads the data. Once the data are downloaded, the app uploads the data to a cloud-based server. The mobile app queries the server for the wear-time estimates and displays them graphically on the mobile device. All data

transfers (brace to app, app to cloud, cloud to app) are encrypted, as are the data stored on the server. The server keeps a record of the transfer details for an audit trail, including the following: Serial number of the sensor in the brace, unique user ID, battery level in the sensor, sensor firmware version, mobile app version, records transferred and time of transfer. The permissions required by the app include: Location, USB storage, and network access, Bluetooth settings and Bluetooth pairing. The app's Privacy Policy (as of July 2, 2019) discusses sharing data from the app with health care professionals via an interactive platform if permission is granted by the user and the provider. This function is not available at this time, and there are no plans to share app data with anyone but the subject during this pilot study. Directions for accessing and using the app will be provided to the families (GSM App Instructions, attached). The server (and the software residing on the server) are managed by Mindset Medical. Green Sun Medical has a Business Associate Agreement with Mindset Medical that satisfies HIPAA requirements.

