Rare adverse events have been reported related to the use of TLSOs.⁷ Most events involve loss of skin integrity (rash, bruise, irritation) due to pressure from the brace on the skin. Some change in the skin is expected in response to the corrective forces, but loss of integrity should not occur. The risk of these events will be mitigated by careful fitting of the GSM brace and by advising subjects to immediately report any areas of discomfort so the brace can be adjusted. In addition, patients using rigid TLSOs have reported issues with body image and self-esteem, depression and anxiety, although it is not clear that these concerns are directly related to brace wear or to the diagnosis itself. There is no reason to believe that these events or concerns would be any more frequent or severe during the use of the GSM brace, and may be less frequent. Subjects will be followed closely via phone calls every 2 weeks and queried about concerns/events related to brace wear.

Study-related Radiation: All subjects will have research-related coronal radiographs while 1) wearing their TLSO at baseline, 2) in the GSM brace after 1 week of wear, and 3) out of the brace after 3 months of wear. Three additional in-brace coronal radiographs may be obtained at the discretion of the orthotist or investigator in order to maximize the fit, correction, and comfort of the brace and/or check the effect of brace modifications. The total number of research-related radiographs will not exceed 6.

Other than ionizing radiation, here are no valid and reliable methods currently available to directly assess the spine's response to a scoliosis brace. The frequency of radiographs during brace treatment for AIS varies, but in general, radiographs are obtained prior to initiation of a brace, in the brace anywhere from the day the brace is fit to 6 months afterward, and then every 4-6 months until criteria for brace discontinuation is met. Since subjects will enter this study at different times during their treatment, we cannot anticipate which, if any, of the radiographs obtained in this study should be considered standard of care. Therefore, all radiographs obtained between consent and Visit 3 will be considered study-related.

A urine pregnancy test will be administered to all subjects who are of child-bearing potential. If the test is positive, the subject will exit the study.

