6.2 PARTICIPANT DISCONTINUATION/WITHDRAWAL FROM THE STUDY

1. Participants will be withdrawn from the study in the event of a positive pregnancy test or reports of a suspected pregnancy.
2. Participants may withdraw voluntarily from the study or discontinue use of the GSM brace at any time. Participants who wish to stop wearing the GSM brace will be instructed to notify study staff so that treatment can be resumed using the TLSO brace.

Participants will be instructed to contact the study staff (PI, orthotist or coordinator) at any time to discuss issues they may be having with the GSM brace or with any other aspect of the protocol. Study staff will attempt to make any modifications to the brace or other aspects of the protocol necessary to mitigate these issues and maintain the participant on protocol.

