6.3 LOST TO FOLLOW-UP

Participants will be considered lost to follow-up if they cease to report for study visits and do not respond to our attempted contacts. Staff will contact participants by phone at 2 weeks after GSM brace initiation and at least monthly to address questions and issues. Subjects will be queried for any questions or concerns, and for the occurrence of anticipated and unanticipated adverse events.

Study staff will accommodate the participants' schedule in order to minimize missed study visits. In the case of a missed visit, staff will attempt contact via three phone calls and/or emails each 1 week apart.

Completion of the questionnaires and diaries will be encouraged but not required.

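### The visit schedule lists no staff safety call between week 10 and Visit 3, so it delivers the two-weekly calls described in the risk section only if Visit 3 falls at week 12

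*Combined protocol and SAP*

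**What the plan says.** Three parts of the protocol set the frequency of staff calls.

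- **Section 5.1.2 (Study Procedures)** is the schedule that sites work from. It has a call 2 weeks after baseline, then "Phone Visits (Weeks 4, 6, 8, and 10 after baseline"), each with a safety check that asks about adverse events. The next scheduled contact is "Visit 3 (3-4 months after baseline, approximately 1 hour"), which has its own safety check. Nothing is listed in between.
- **Section 5.2.1 (Known Potential Risks)** says "Subjects will be followed closely via phone calls every 2 weeks", with a query about brace-related concerns and events. No end date is given.
- **Section 6.3 (Lost to Follow-up)** says staff will phone "at 2 weeks after GSM brace initiation and at least monthly". These calls include an adverse event query: "Subjects will be queried for any questions or concerns, and for the occurrence of anticipated and unanticipated adverse events".

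Other routes for adverse events run alongside the calls. Section 7.3.4 solicits events at visits, at scheduled calls and, as often as daily, by self-report. The diary asks about pain and discomfort (section 5.1.2, Questionnaires), but under section 6.3 "Completion of the questionnaires and diaries will be encouraged but not required". Section 5.2.1 relies on "advising subjects to immediately report any areas of discomfort so the brace can be adjusted", and section 6.2 adds "Participants will be instructed to contact the study staff (PI, orthotist or coordinator) at any time".

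**The concern.** Safety is the first primary objective (section 2). The subjects are aged 10-15, and the study rationale says the brace had so far been tested only in the lab on healthy volunteers. The risk section presents the two-weekly calls as close follow-up, but the schedule stops them at week 10 while letting the next visit fall as late as 4 months. A site that follows section 5.1.2 to the letter would therefore not do what section 5.2.1 describes for any subject whose Visit 3 is later than week 12.

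What is at stake is timeliness. A pressure area, pain or a fit problem that the subject does not volunteer would be asked about later than the risk section implies. The calls at weeks 4 to 10 also remind families to complete and return the diaries, so that prompt stops as well.

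**Working it through.** The documents state no interval to reproduce, so this is calendar arithmetic on the stated schedule.

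**Inputs**
- Last scheduled call: week 10 (section 5.1.2).
- Visit 3: 3-4 months after baseline (section 5.1.2).
- Interval in the risk section: 2 weeks (section 5.2.1).
- Minimum contact: at least monthly (section 6.3).
- Length of a month: not defined, so an assumption. Two values are used: 4 weeks, and 365.25 / 12 / 7 = 4.348 weeks.

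**Step 1. Scheduled gap = Visit 3 week − 10**

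| | Visit 3 at 3 months | Gap | Visit 3 at 4 months | Gap |
|---|---|---|---|---|
| 4-week months | 3 × 4 = 12 | 2 | 4 × 4 = 16 | 6 |
| Calendar months | 3 × 4.348 = 13.04 | 3.04 | 4 × 4.348 = 17.39 | 7.39 |

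With 4-week months, the 2-week interval is met at week 12 and at no later date. With calendar months, even the earliest permitted visit exceeds it, by 3.04 − 2 = 1.04 weeks.

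**Step 2. Effect of the monthly contact in section 6.3**

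This depends on how a month is counted, which section 6.3 does not say.

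- *No more than one month since the last call.* Longest interval = the smaller of the gap and one month. With 4-week months this is 2 to 4 weeks; with calendar months it is 3.04 to 4.35 weeks. The upper end is still about twice the 2 weeks in section 5.2.1.
- *One contact in each month from baseline, with Visit 3 able to count.* With 4-week months, the week 10 call serves month 3 (weeks 8-12) and a Visit 3 at week 16 serves month 4 (weeks 12-16). No further call is due, and the gap stays at 6 weeks. With calendar months, week 10 lies in month 3 (weeks 8.70-13.04) and a visit at week 17.39 closes month 4. The gap stays at 7.39 weeks.
- *Monthly calls counted from the week 2 call.* With calendar months the calls fall at 2 + 2 × 4.348 = 10.70 and 2 + 3 × 4.348 = 15.04. The longest interval is 13.04 − 10.70 = 2.35 weeks (before rounding) for the earliest Visit 3, and 15.04 − 10.70 = 4.35 weeks (before rounding) for the latest.

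**Step 3. With two-weekly calls continued to Visit 3**

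- 4-week months: no extra call for a week 12 visit; weeks 12 and 14 for a week 16 visit. That is 0-2 calls.
- Calendar months: week 12 for a visit at 13.04; weeks 12, 14 and 16 for a visit at 17.39. That is 1-3 calls.
- The longest interval inside the visit window is 2 weeks under both definitions.

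**The case against.** The strongest reply is that the nominal schedule has no gap. Calls at weeks 2 to 10 followed by Visit 3 at week 12 form an unbroken two-weekly series. Section 5.6, which counts 10 additional weeks in the 3-month period, fits a 12-week plan. On that view the sentence in section 5.2.1 summarises the schedule and does not promise anything for late visits. Section 6.3 covers the late-visit case with a monthly call. No section makes 2 weeks a safety threshold, and section 7.2.1 describes most skin problems as mild and relieved by minor adjustment. After Visit 3 the protocol moves to adverse events found at routine clinic visits or through other communications, so less frequent querying later in wear is accepted.

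Much of this stands. At week 12 there is no discrepancy, and the documents do not say how often Visit 3 is later. But the window runs to 4 months, and the monthly call is absent from the schedule that sites follow. It also leaves an interval of about 4 weeks on its stricter reading and up to 6 or 7.4 weeks on its looser one.

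Two stronger readings are tempting, and the documents support neither. A reader might infer that subjects go unmonitored between week 10 and Visit 3. They do not: self-report by diary, immediate reporting of discomfort and open access to staff all continue, although the diary is voluntary. A reader might also infer from section 6.3 that the interval is firmly limited to about 4 weeks. That holds only if a month is counted from the last call.

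**Conclusion.** The inconsistency is real and small. Section 5.1.2 leaves a scheduled gap in staff safety calls of 2-6 weeks (4-week months) or 3.0-7.4 weeks (calendar months), against the 2 weeks in section 5.2.1. The monthly contact in section 6.3 reduces the upper end to about 4-4.35 weeks, on the assumption that it means no more than one month since the last call.

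The consequence is later staff-solicited detection for subjects whose Visit 3 falls after week 12. It does not follow that events are lost. No endpoint or analysis depends on the calls, and section 8.4 plans no formal hypothesis testing. It is a worthwhile improvement of low severity.

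**What to change.** In section 5.1.2, extend the heading of the later phone visits so that, after week 10, it also lists weeks 12, 14 and 16, each to be made only if Visit 3 has not yet occurred. The content of the call, including the safety check, stays the same. Sections 5.2.1 and 6.3 need no edit: the schedule would then match the first, and two-weekly calls satisfy the monthly minimum in the second on any reading.

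The cost is one line of wording and 0-3 short calls per subject, none if Visit 3 is at week 12. For the maximum of 30 completers in section 8.1 that is at most about 3 × 30 = 90 calls. No new staff or procedure is needed; the downside is a small added burden on sites and families.

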5 STUDY INTERVENTION

5.1.1 STUDY INTERVENTION SUMMARY FLOWSHEET

5.1.2 STUDY PROCEDURES

Immediately After Consent is Signed and Received by Study Team

The following will be sent to Green Sun so that an appropriately-configured GSM brace can be made for the subject:

- 1) A de-identified copy of the most recent 3D scan of the patient's torso (tagged with a study ID number)
- 2) The individualized treatment plan devised by the PI which specifies the location and direction of applied forces (e.g. push on the patient's left axilla, push on the patient's right rib cage roughly 4 inches lateral of midline around T9) and tagged with a study ID number

The Baseline Visit will be scheduled approximately 2 weeks after consent is signed and the 3D scan and treatment plan have been sent to Green Sun to allow Green Sun time to fabricate the brace.

Instructions for Radiographs

1. All study-related radiographs will be obtained using the EOS® Imaging system Micro Dose protocol (when available). If an EOS system is not available, please see **Additional Information on Assessments**, Radiographs and Assessments, and **5.2.1 Risks** for further information).
2. The number of study-related radiographs is NOT to exceed 6.
3. Three radiographs are required:
 - a. In the TLSO (Baseline Visit 1)
 - b. In the GSM (Visit 2)
 - c. Out of brace (Visit 3)
4. A maximum of **3** optional in-brace radiographs may be taken at any time prior to Visit 3 to maximize the fit, correction and comfort of the GSM brace.

Baseline Visit 1 (approximately 2 hours)

1. A urine pregnancy test will be conducted. Pregnant subjects will exit the study.
2. Completion of the Brace Questionnaire and the Italian Spine Youth Quality of Life (ISYQOL) questionnaire (5 minutes)
3. Assessments while wearing current TLSO
 - a. Vital capacity using Spiropet spirometer (average of 3 trials, 5 minutes)
 - b. Measurement of spine range-of-motion (flexion, extension, rotation) using a tape measure (5 minutes)

- c. In-brace standing coronal full-spine radiograph (5 minutes)

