8.4 STATISTICAL ANALYSES

This is a pilot study and no formal hypothesis testing will be done.

Descriptive statistics of selected variables will be calculated.

Primary Aims

1. Safety of the GSM brace: Summary of all adverse events; number and nature of adjustments made to the GSM brace
2. Performance of the GSM brace:
 - a. Difference between in-brace Cobb angle measurements obtained in each brace
 - b. Difference in out of brace Cobb angles (pre- and 3 months post-GSM brace)
 - c. Average hours of wear per day relative to the prescription and to historical wear data (from chart and temperature monitor)
 - d. Change in BrQ and ISYQOL scores baseline to 3-month visit; summary of GSM acceptability during various activities and qualitative analysis of free text entries recorded in GSM Brace Diary

Secondary Aims

1. Difference in range-of-motion testing between TLSO and GSM brace
2. Difference in vital capacity testing between TLSO and GSM brace

3. Correlation of accelerometer data and temperature monitor data; development and testing of an algorithm to convert accelerometer data to an estimate of the average hours of wear per day.

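### Visit 3 lists the BrQ and ISYQOL after the film and Cobb measurement, whereas Baseline lists them before the study film, so the primary change score may pick up reaction to the same-day result

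*Combined protocol and SAP*

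**What the plan says.** Section 5.1.2 (Study Procedures) gives a numbered list for each visit. At Baseline Visit 1 the pregnancy test is item 1 and the BrQ and ISYQOL are item 2. The TLSO assessments are item 3, with the in-brace film last among them at 3c, and the GSM fitting is item 4.

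At Visit 3, item 1 is "Standing coronal full-spine radiographs out of the brace and measurement of the Cobb angle". Items 2 and 3 are the temperature-monitor download and diary collection. Item 4 is "Completion of the Brace Questionnaire and the Italian Spine Youth Quality of Life (ISYQOL) questionnaire". Item 7, the Performance Check, compares the new angle with the out-of-brace film from before enrolment. If the limit is exceeded, the instruction is "If not, the subject will resume use of the TLSO". Otherwise item 7b applies: "If curve stabilization is seen, subjects may opt to continue the GSM brace or resume use of their TLSO based on subject and parent preferences".

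Section 7.1 makes the change in these questionnaire scores a primary performance measure. Section 8.4, primary aim 2d, summarises it as "Change in BrQ and ISYQOL scores baseline to 3-month visit". Section 3.1 describes an open-label design with within-subject comparison, and section 5.3 says neither subjects nor assessors can be blinded to the type of brace.

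**The concern.** A change score is easiest to interpret when both ends are collected under the same conditions. Here the Baseline questionnaires come ahead of that visit's film. The Visit 3 questionnaires come after a film whose angle has already been measured and which bears on whether the subject may stay in the GSM brace. An adolescent who has just heard that her curve is stable, or that it has progressed, may answer quality-of-life questions differently from one who has not heard. The same applies to the item added for this study on how much she likes her brace.

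With no concurrent group, nothing in the design would cancel such a reaction, and it would pass directly into the mean change. Acceptability relative to the rigid TLSO is central to the study rationale in section 1.1, and section 3.1 says the pilot is meant to support a later pivotal trial. The plan does not ask sites to record the order of assessments or when the result was disclosed, so the analysis could not separate the effect afterwards.

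**Working it through.** The plan gives no figure to reproduce. It states no standard deviation, effect size or sample-size calculation for the BrQ or ISYQOL. The check is therefore a comparison of the two lists in section 5.1.2.

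| Step | Baseline Visit 1 | Visit 3 |
|---|---|---|
| BrQ and ISYQOL | item 2 | item 4 |
| Study film | item 3c (in TLSO) | item 1 (out of brace) |
| Cobb measurement named in the film item | no | yes |
| Decision based on that visit's angle | none | item 7 |

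1. **Order.** Baseline runs questionnaires, then film. Visit 3 runs film and angle, then questionnaires, then decision. The asymmetry is confirmed.

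2. **Is the angle available before item 4?** If the list is followed as written, yes, because item 1 includes the measurement. Section 5.3 assigns it to the site investigator or a delegate, with verification by the medical advisor at an unstated time.

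3. **Does the subject know it by then?** The documents do not say. No section requires disclosure before item 4 and none prevents it. The only step that acts on the angle comes after the questionnaires.

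4. **Form of the bias.** Let p be the share of subjects told their result before item 4, and d the mean score shift that hearing it causes among them. Baseline has no matching same-day term, because the questionnaires precede the film. So

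   expected observed change = expected change without disclosure + p × d.

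   The documents give neither p nor d. If p = 0 the added term is 0. If p > 0 its sign is the sign of d, which depends on the mix of good and bad news and on how subjects react. No numerical range can be derived.

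5. **What reordering would leave in place.** Inclusion criterion 3 in section 4.1 refers to an out-of-brace x-ray from the previous 6 months, and criterion 2 requires at least 5 months in a TLSO, so subjects may already know their curve status at Baseline. Anyone who reaches Visit 3 has also passed the Visit 2 in-brace film and its continue-or-exit check. Moving the questionnaires removes only the same-day result.

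**The case against.** The strongest objection is that disclosure is assumed. Taking and measuring a film is not the same as telling the family the answer, and the step that would naturally involve telling them is item 7, after the questionnaires. This stands: a reader might infer that the change score does mix in reaction to the result, but the documents support only that it may.

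Nor does the plan say that the numbering is a required sequence. The optional app appraisal at Baseline is item 8, after the subject is listed as sent home at item 6, so that list is not strictly chronological. The section 5.1.1 flowsheet is not readable in the available text and cannot settle the matter. This also stands, although the clinical core of the Baseline list (pregnancy test before film, TLSO tests before GSM fitting, fitting before GSM tests) works only in order, and a coordinator could reasonably read Visit 3 the same way.

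A reader might also infer that the radiographic result (2b) and the patient-reported result (2d) stop being separate evidence. That goes too far. Aim 2d also draws on a daily diary returned during follow-up, and entries made before Visit 3 cannot be affected by the Visit 3 film.

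Finally, the analysis is descriptive and no hypothesis test is planned. No error rate is at stake, which lowers the priority. It does not remove the point, because the descriptive mean change is itself the reported result.

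**Conclusion.** The point holds in a limited form. The listed order differs between the two ends of a primary change score, and the plan contains no safeguard against the Visit 3 result reaching the subject before she answers. The BrQ/ISYQOL change may therefore include reaction to that day's film. A reader might infer a bias in the brace's favour on the expectation that most news will be good, but the documents give no basis for a size or a direction.

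The conclusion rests on two assumptions: that some sites follow the list as written, and that some subjects learn the angle before item 4. If the second fails for every subject, the effect is zero. Knowledge from earlier films remains in any case. The priority is minor; the case for acting is that the same-day component is avoidable at almost no cost and cannot be corrected afterwards.

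**What to change.** In section 5.1.2, move the BrQ, the ISYQOL and the added brace-liking item to the start of Visit 3, to match Baseline. State that they are completed before the radiograph, or at least before any Cobb result or continuation decision is discussed with the subject or parent. Add a field to the visit form recording whether this order was kept.

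The change should stop there. Moving the diary hand-in would achieve little, because that item only collects a record kept daily. The end-of-treatment questionnaires are not suited to the same rule: Cobb angle is one of the criteria that can end treatment and so trigger that assessment, and the time point lies outside the baseline-to-3-month analysis.

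The cost is a sentence or two of protocol wording and one form field. It adds no visit, procedure or radiation, and leaves the sample size and every clinical rule unchanged.
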